6.1. Missing data

When analyses were performed based on the ITT population, multiple imputation (MI) will be performed for both primary and secondary outcomes based on the baseline variables of patient characteristics and the outcome in question.

Referencer

2. Fisher AG, Jones, K B. Assessment of Motor and Process Skills: Skills, Development, standardization and administration: Manual. Fort Collins, CO: Three Star Press; 2010.
3. Fysioterapeuter D. Functional Recovery Score (FRS). 2018.

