3.1. Sample size calculation

Statistical power calculation is based on the minimum clinically important difference (MCID) for motor skills in AMPS, which is 0.3 logits (2). The power is set to 0.8 and the standard deviation (SD) is 0.50, which gives a sample size of 90 persons (2). Because of expected dropout, 54 elderly with hip fracture are therefore included in each group.

4. Outcomes

This section will present the outcomes investigated to answer the study aims, objectives and hypothesis.

The analyses are described in section 6 Analyses.

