5.1. Populations

Intention to treat (ITT): All randomised participants. This will be the primary population for the analysis.

Per Protocol (PP): All randomised participants completing the whole study period (complete cases). Analysis of the population is seen as a sensitivity analysis to investigate whether conclusions are sensitive to the assumptions that missing data were missing at random.

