5.2 Subgroups

Due to Covid-19 some participants may not have received the entire intervention at home and therefore subgroup analysis restricted to participants received at least three of the planned visits in own home.

6. Statistical analysis

The primary analysis will be a mixed effect model where group (intervention and control) and municipality are fixed, and the patient is random, assuming dropout is at random. The score at the end of rehabilitation after 3 months will be analysed unadjusted and adjusted for baseline score, age, municipality, gender, fracture and type of operation.

The estimated difference in mean change from baseline to 3 months follow-up and the corresponding 95 % confidence interval (CI) will be presented. Stata (StataCorp. 2019) will be used for the statistical analysis.

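### Section 6.1 does not name randomised group among the imputation inputs; followed as written, a real treatment effect shrinks by roughly the fraction of 3-month scores that are missing

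*SAP*

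**What the plan says.** SAP section 6.1 is one sentence. For analyses in the intention-to-treat (ITT) population, "multiple imputation (MI) will be performed for both primary and secondary outcomes", and the imputation is "based on the baseline variables of patient characteristics and the outcome in question". No other section adds an input or says that imputation is run separately by arm.

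The rule governs the main result, because section 5.1 defines the ITT population as "All randomised participants. This will be the primary population for the analysis".

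Section 6 states the model fitted: "The primary analysis will be a mixed effect model where group (intervention and control) and municipality are fixed", with patient as a random effect. The 3-month score is analysed both unadjusted and "adjusted for baseline score, age, municipality, gender, fracture and type of operation". Results are reported as an estimated difference with a 95% confidence interval.

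Section 5.1 also plans a complete-case analysis, there called per protocol, to test sensitivity to the missing-at-random assumption.

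**The concern.** An imputation model should contain at least the variables of the analysis model, and above all the one whose effect is being estimated. Section 6.1 gives a positive list of inputs, and randomised group fits neither entry. It is not a baseline patient characteristic, since section 3 places randomisation after the baseline test, and it is not the outcome.

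If the list is followed literally, an intervention participant and a control participant with the same baseline profile get imputed 3-month scores from the same distribution. Those scores contain no treatment difference, and mixing them with the observed scores dilutes the difference that is really there. This needs no informative or unequal dropout, so the assumption in section 6 that dropout is at random gives no protection.

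At stake are the size of the primary estimate and the power that the dropout allowance in section 3.1 was meant to preserve.

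**Working it through.** **Inputs.** From section 3.1: difference 0.3 logits, SD 0.50, power 0.8, 90 persons needed, 54 per group included. From section 3: 1:1 allocation. Assumed, because the SAP does not state them: two-sided alpha 0.05 (in line with the 95% interval in section 6), the dropout rate, and the correlation between baseline and 3-month scores.

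**1. The plan's own sample size.** The SAP says "The power is set to 0.8 and the standard deviation (SD) is 0.50, which gives a sample size of 90 persons". The normal approximation gives n per arm = 2 × (1.96 + 0.84)² × 0.50² / 0.30² ≈ 43.6, so 44 per arm and 88 in total. The t-test version gives 44.6, so 45 per arm and 90 in total. The stated figure is reproduced, with power 0.804 at 45 per arm. A one-sided test would need 70, which does not fit.

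**2. The implied dropout.** The SAP says "Because of expected dropout, 54 elderly with hip fracture are therefore included in each group", which is 2 × 54 = 108. Then 1 − 90/108 = 16.7%. The same total also arises from adding 20% (90 × 1.20 = 108). Neither rate is stated, so a range is used below.

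**3. The dilution, equal dropout.** Let δ be the true difference, d the missing fraction in each arm, and 0 the control mean. The observed scores pooled over arms have mean δ/2, and imputed scores have that expectation in both arms. After imputation:

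- intervention mean = (1 − d)δ + d·δ/2
- control mean = d·δ/2
- difference = (1 − d)δ

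Baseline covariates are balanced by randomisation and do not change this in expectation. With δ = 0.30:

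- d = 5%: 0.285
- d = 10%: 0.27
- d = 16.7%: 0.25
- d = 20%: 0.24
- d = 25%: 0.225

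**4. The dilution, unequal dropout.** Let p = (1 − d_I)/[(1 − d_I) + (1 − d_C)]. The difference becomes δ[(1 − d_I) + p(d_I − d_C)]. For 8.3% in intervention and 25% in control, p = 0.55 and the result is 0.30 × (0.917 − 0.092) ≈ 0.25. With the rates reversed, p = 0.45 and the result is 0.30 × (0.75 + 0.075) ≈ 0.25. Simulation gave 0.249 and 0.246.

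**5. Simulation of estimate and power.** Set-up: 54 per arm, SD 0.50, true effect 0.30, missing completely at random, normal-regression imputation with 20 imputations, Rubin's rules with small-sample degrees of freedom, baseline-adjusted linear model, 2,000 runs. The estimates shown are for correlation 0.5.

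| Missing | Estimate without / with group | Power without / with, correlation 0 | Power without / with, correlation 0.5 |
|---|---|---|---|
| 5% | 0.284 / 0.299 | 81% / 84% | 92% / 94% |
| 10% | 0.272 / 0.302 | 76% / 83% | 88% / 92% |
| 16.7% | 0.252 / 0.302 | 68% / 81% | 81% / 90% |
| 25% | 0.225 / 0.301 | 52% / 74% | 65% / 85% |

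Separate simulations of the 16.7% case gave estimates of 0.246 to 0.252 without group. Power without versus with group was 63–68% versus 78–81% at correlation 0, and 79–81% versus 88–90% at correlation 0.5. This spread exceeds the Monte Carlo error of about 1 point, so absolute power should be read to within a few points. The loss is steadier: 12 to 15 points at correlation 0 and 8 to 10 at correlation 0.5.

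**6. No true effect, and complete cases (16.7% missing).** With no true effect and group omitted, the mean estimate is 0.00 and the rejection rate is 1.6% to 2.0%, against 3.9% with group included. Complete cases with a true effect of 0.30 give 0.30, with power 81% (correlation 0) or 91% (correlation 0.5).

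**The case against.** The strongest reply is that section 6.1 is a one-sentence summary and does not say that only the named inputs are used. An experienced analyst might include group or impute by arm and regard that as consistent with the text. This stands in part: group is not expressly excluded. But the sentence names its inputs, nothing elsewhere completes them, and a literal reader would leave group out.

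A second reply is that section 6 reads like a mixed model fitted to observed data, which contains group and would not be diluted. That is true of such a model. However, section 6.1 says imputation will be performed for the ITT analyses, and those are primary, so this reading does not remove the problem.

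Third, the power loss depends on an inferred dropout rate and on how well baseline predicts outcome. This is right: at correlation 0.5 and 16.7% missing, power without group is still about 80%. The shrinkage of the estimate is the same at either correlation, and an unadjusted analysis gains nothing from baseline.

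Fourth, the error is conservative, and the planned complete-case analysis could expose it. Both points are correct. Yet the SAP reports an effect size with an interval, and an estimate biased towards zero misleads whether or not it is significant. Section 5.1 presents the complete-case analysis as a check on missing at random, so a gap caused by the imputation model could be misread as failure of that assumption. Nor would the check repair the primary estimate.

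Finally, some of the analysis covariates are arguably already covered by the wording on patient characteristics. That is fair. Naming them is clarification, and group is the substantive omission.

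**Conclusion.** The concern holds and should be corrected before the ITT analysis is run. Followed as written, section 6.1 yields about (1 − d) times the true effect when a fraction d of 3-month scores is missing. At the inferred 16.7%, a true effect equal to the SAP's 0.3-logit threshold would be reported as about 0.25, below that threshold. Between 5% and 25% missing, the estimate runs from about 0.28 to 0.22. At 16.7% the power loss is roughly 8 to 15 points, which takes power below the planned 80% if baseline does not help and leaves it near 80% at correlation 0.5.

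These figures assume that the list of inputs is taken as complete, that scores are missing completely at random, a two-sided 5% test, SD 0.50, and a dropout rate that the SAP does not state. The bias is towards no effect only. If there is no true effect, there is no bias and no excess of false positives. If few scores are missing, the harm is small.

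**What to change.** In section 6.1, state either that imputation is carried out separately by randomised group or that group is a predictor in every imputation model, for primary and secondary outcomes alike. In the same sentence, name the baseline value of the outcome, municipality, and the other covariates of the adjusted model in section 6.

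The cost is one phrase in the SAP and, for imputation by arm, a by(group) option in Stata's mi impute. A masked group code keeps the analysis blinded as section 3 requires. No new data are needed.

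In simulation at 16.7% missing, including group restores the mean estimate to about 0.30.

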4.1 Primary outcome

The primary outcome (AMPS) will be assessed on the third to fifth post-operative day at the hospital (2). AMPS, is a standardized observation-based evaluation tool to measure a persons observed quality of ADL task performance in terms of physical effort and/or fatigue, efficiency, safety and independence (2). Furthermore, the AMPS test will be performed, after completed rehabilitation at 3 months follow-up to identify older adults with hip fractures challenges with Personal Activity of Daily Living (PADL) and Instrumental Activity of Daily Living (IADL).

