4.2 Secondary outcomes

Functional Recovery Score (FRS) (3), Health-related QoL: European Quality of Life Scale (EQ-5D) (4) and Verbal Rating Scale (5).

Other data collected: Age, gender, type of fracture, waiting time for surgery, length of stay in acute hospital, marital status, type of dwelling, comorbidity (Charlson Index), 30-days mortality, physical therapy and occupational therapy services, level of education, warranted community-based assistance, inpatient and outpatient treatment since last assessment, usage of home-based services and pain score.

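### Section 6.1 imputes each outcome on its own from baseline data, does not name randomised group, and makes no use of the other 3-month outcomes

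*SAP*

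**What the plan says.** SAP section 6.1 is the only rule on missing data. For the ITT population, "multiple imputation (MI) will be performed for both primary and secondary outcomes", and the imputation is "based on the baseline variables of patient characteristics and the outcome in question". It does not list the baseline variables, does not mention randomised group, and does not say whether the outcome in question means its baseline value, its 3-month value or both.

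Four other parts of the SAP bear on this:

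- Section 5.1 makes ITT the primary population. It defines the per-protocol set as the completers and uses it to check sensitivity to the missing-at-random assumption.
- Section 6 describes a mixed model in which "the patient is random, assuming dropout is at random". The 3-month score is analysed "unadjusted and adjusted for baseline score, age, municipality, gender, fracture and type of operation".
- Section 4.1 gives AMPS a single post-baseline assessment, "after completed rehabilitation at 3 months follow-up".
- Section 4.2 names FRS, EQ-5D and the Verbal Rating Scale as secondary outcomes. It also lists other collected data, including length of acute stay and "marital status, type of dwelling, comorbidity (Charlson Index), 30-days mortality".

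**The concern.** An imputation helps when it uses information that the analysis model lacks. The section 6.1 wording raises three doubts about that.

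1. With one follow-up assessment, imputing the 3-month score from the variables the analysis already adjusts for adds nothing. The adjusted ITT result and the adjusted complete-case result would then agree almost by construction, and that agreement could be mistaken for support for missing at random.
2. Group is not named. An imputation model without it draws the missing values of both arms from one common regression, which pulls the treatment difference towards zero.
3. AMPS requires an observed task performance. If a patient misses it but still provides FRS or EQ-5D, those values carry information on 3-month function that baseline data do not, and the rule sets them aside.

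At stake is the primary ITT estimate, judged against a minimum important difference of 0.3 logits.

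**Working it through.** **Inputs.** From SAP section 3.1: difference 0.3 logits, SD 0.50, power 0.8, 90 persons before dropout, 54 per group after. Assumed, because the SAP does not give them: two-sided alpha 0.05; correlation 0.5 between baseline and 3-month AMPS; residual correlation 0.5 to 0.7 between 3-month AMPS and FRS; and the missingness mechanism.

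**Step 1: the plan's own figure.** Per arm, n = 2 × (1.96 + 0.842)² × 0.50² / 0.3² = 2 × 7.85 × 0.25 / 0.09 = 43.6, so 44. The t distribution gives 44.6, so 45 per arm and 90 in total, as stated. With 2 × 54 = 108 randomised, the implied missing share is 1 − 90/108 = 0.167.

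**Step 2: imputation set equal to adjustment set plus group.** Let b be the least-squares fit to the observed patients. With many imputations, the missing scores average to their fitted values under b. Refitting the same model to observed and imputed patients together minimises two sums of squares, and b minimises both, so the estimate is unchanged. Simulation agrees (1,500 trials, n = 108, about 17% missing, truth 0.30): imputation 0.2975 (SE 0.0945), adjusted complete cases 0.2978 (SE 0.0941), correlation 0.997.

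**Step 3: group left out.** Imputed patients then show almost no difference between arms, given baseline. The estimate is about (1 − 0.167) × 0.30 + 0.167 × 0 = 0.25. Simulation gives 0.247 to 0.249 when missingness is unrelated to outcome. With FRS included but group still omitted, it is 0.27 to 0.28.

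**Step 4: a further baseline predictor outside the section 6 covariates** (assumed coefficient 0.5 in SD units). If dropout depends on it in one arm only, adjusted complete cases give 0.369 and imputation with the predictor gives 0.302. If dropout depends on it equally in both arms, neither is biased, and the SE is 0.0905 with the predictor against 0.0925 for complete cases.

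**Step 5: adding another 3-month outcome, group included.**

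Precision, when missingness creates no bias:

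| Residual correlation | Share of missing-AMPS patients with the other outcome | SE, baseline only | SE, with other outcome |
|---|---|---|---|
| 0.7 | 0% | 0.0945 | 0.0947 |
| 0.7 | 25% | 0.0928 | 0.0915 |
| 0.7 | 50% | 0.0928 | 0.0908 |
| 0.7 | 100% | 0.0918 | 0.0885 |
| 0.5 | 100% | 0.0915 | 0.0901 |

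The largest gain is 1 − 0.0885/0.0918 = 3.6%.

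Bias, when control-arm missingness depends on 3-month function and intervention-arm missingness does not (truth 0.30, residual correlation 0.6):

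| Driver of missingness | Baseline plus group | FRS known for half | FRS known for all |
|---|---|---|---|
| FRS-type function | 0.25 | 0.28 | 0.30 |
| AMPS itself | 0.22 | 0.23 | 0.25 |

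For FRS-driven missingness at residual correlations 0.5 and 0.7, baseline plus group gives 0.256 and 0.241. FRS known for half gives 0.279 and 0.275; FRS known for all gives 0.297 and 0.300. With the same mechanism in both arms, baseline plus group already gives 0.30.

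**The case against.** The strongest case on the other side has four parts.

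- **The wording is loose rather than restrictive.** A reader might infer that the imputed ITT estimate can recover nothing from dropouts. The SAP does not support that. Section 6.1 does not confine the baseline variables to the section 6 covariates, and section 4.2 lists others, such as the Charlson Index, dwelling and education. Step 4 shows that such a variable can matter. The equality in step 2 also concerns the adjusted analysis, and an unadjusted one is planned too. This objection stands, so the point is conditional on which variables enter.
- **Separate missingness of AMPS is not documented.** The SAP gives no mode of collection for FRS or EQ-5D and speaks only of dropout, which would normally remove every 3-month measure. Inpatient and outpatient treatment is recorded since the last assessment, so it may be lost at the same visit. This also stands: the gain from other outcomes may be zero.
- **The larger correction depends on the mechanism.** Full return to 0.30 needs missingness explained by FRS and FRS known for everyone. If AMPS drives missingness, most of the bias remains. Differential missingness between arms is assumed, not shown. A bias of 0.05 is also only about half the SE of 0.09. Nobody should infer that the trial's estimate will be biased by this amount.
- **Imputing each outcome from baseline data is a valid missing-at-random method.** It is, provided group is included and baseline data plus group explain the missingness. Section 6.1 secures neither condition.

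Nor does silence on group show that group will be omitted; it shows only that the text would permit it.

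**Conclusion.** The point holds in conditional form. Three statements can be made, in decreasing order of certainty.

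1. If group is omitted from the imputation model, the estimate shrinks by about the missing share, from 0.30 to about 0.25 at 17%. This needs no differential dropout.
2. If the imputation variables are no more than the adjustment covariates plus group, the adjusted ITT and adjusted complete-case estimates coincide apart from simulation noise. Their agreement then says little about missing at random, since both rest on it.
3. Using FRS or EQ-5D where AMPS is missing can remove part or all of a bias of roughly 0.05 to 0.08 logits. This rests on the assumed correlations, on missingness that differs between arms, and on those outcomes being observed. Where there is no bias to remove, the benefit is a 0 to 4% smaller SE. Where all outcomes are missing together, there is none.

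It is worth correcting because the remedy is cheap and the SE did not materially rise in the scenarios examined, but it does not show that the planned result is wrong.

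**What to change.** Replace the section 6.1 rule with one chained-equations imputation, and list its variables:

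- randomised group, named explicitly because the section 6 covariate list does not contain it, or imputation run separately by arm;
- all covariates of the adjusted model;
- AMPS, FRS, EQ-5D and the Verbal Rating Scale at baseline and 3 months, where collected;
- a short list of available auxiliaries, such as length of acute stay and the Charlson Index.

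Analyse every ITT outcome from that one set of imputed data. State how many patients with missing AMPS have each other 3-month outcome, since the gain depends on it. The complete-case comparison should no longer be presented as a check on missing at random; an analysis that shifts the imputed values by stated amounts would serve that purpose.

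The cost is a change of SAP wording and some model-building work. The outcomes and auxiliaries named are already on the SAP's lists. The drawback is a larger imputation model at n = 108, more so with 54 per arm if run by arm, so the auxiliaries should be few.
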